6.8 Plan to Minimize Loss-to-Follow-up

[figure not shown]
The sample size of up to 300 subjects for this study (minimum of 250) is based on the assumption that over the course of 5 years there will be at least 20% attrition due to Loss-to-Follow-up. All subjects will be offered reimbursement for completing each planned visit. Note that the amount of reimbursement is limited by each Institutional Review Board (IRB).

As part of the informed consent, patients will be asked to agree to follow-up evaluations out to 5 years after Alair treatment. Each subject will be asked to provide an Emergency contact and contact information for mother (if alive) and a nearest living family member who could be used as alternatives to reach the subject. In addition, subject's will be informed that in the event they fail to respond to written communication in the form of letters by recorded delivery, the Site with support from the Sponsor (Asthmatx, Inc.) will enlist the help of a search agency to confirm the subject's contact information.

Sites will be asked to remind subjects that being the first device based procedure for treating asthma, the commitment of the subjects to their participation for the full 5 years is important in understanding all aspects of the Alair treatment.

Figure 3 outlines the steps that will be taken to contact any subject who misses the planned annual follow-up visit so as to ensure adequate follow-up.

Figure 3: Steps to Contact Subjects for Annual Follow-up Visits

In the event that a letter is returned as undeliverable, Asthmatx will enlist the aid of a search agency to confirm the subject's contact information. If existing contact is valid, one more attempt will be made with certified mail within 30 days before the subject is considered as "unable to contact". If new contact information is obtained, contact will be attempted via 2 recorded delivery mails before the subject is considered as "unable to contact". In the event that a subject is Lost-to-Follow-up, their status at the last contact will be reported.

If needed, the Sponsor will offer to cover travel and housing costs for a subject who has relocated to a new city in order for them to return to the clinical study site to complete their annual follow-up evaluations. Alternatively subjects will be allowed to continue follow-up at the closest study site to their new location.

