7.3.9 Near-Term Follow-up

- Contact subject via telephone on Day 1, Day 2, and Day 7 after the treatment session to assess recovery.
- Remind subject to contact Investigator or a member of the clinical study staff at the Site if they experience any of the following:
 - Difficulty in breathing.
 - Night awakenings due to asthma symptoms.
 - Any changes in maintenance asthma medications.
 - Need to be seen by a physician prior to the next scheduled visit.
 - Any adverse events.

7.3.10 2-Week Follow-up (2 Weeks \pm 4 days after Treatment Session 1 and 2)

Examine the subject and perform the following evaluations:

- Focused physical exam including vital signs (heart rate, blood pressure, temperature, respiratory rate, SpO₂) and breath sounds.
- Review asthma symptoms, exacerbations, and asthma medication use.
- Solicit adverse events since last follow-up (See Section 8.0).
- Review Emergency Room visits for respiratory symptoms since last contact.
- Review hospitalizations for respiratory symptoms since last contact.
- Perform physical examination (including body weight).
- Pre-bronchodilator spirometry following a 12-hour abstinence from long-acting β_2 -agonist and a 4-hour abstinence from short-acting β_2 -agonists
- Post-bronchodilator spirometry 15 minutes after the administration of 4 puffs (total 400 μ g) of albuterol via spacer.
- If a subsequent treatment session is to be completed, see Section 7.3.6 and Section 7.3.7.

7.3.11 6-Week Follow-up (6 Weeks \pm 1 Week after last Bronchoscopy Session)

Examine the subject and perform the following evaluations:

- Focused physical exam including body weight, vital signs (heart rate, blood pressure, temperature, respiratory rate, SpO₂) and breath sounds.
- Review asthma symptoms, exacerbations, and asthma medication use.
- Solicit adverse events since last contact.
- Perform pre- and post-bronchodilator spirometry. Pre-bronchodilator spirometry following a 12-hour abstinence from long-acting β_2 -agonist and a 4-hour abstinence from short-acting β_2 -agonists.
- Review emergency room visits for respiratory symptoms since last contact.
- Review any hospitalizations for respiratory symptoms since last contact.

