7.3.12 3-Monthly Follow-up Phone Contact (3 Months \pm 2 Weeks, 6 Months \pm 2 Weeks, 9 Months \pm 2 Weeks, 15 Months \pm 2 Weeks, and 18 Months \pm 2 Weeks, 21 Months \pm 2 Weeks, 27 Months \pm 2 Weeks, 30 Months \pm 2 Weeks, 33 Months \pm 2 Weeks, 39 Months \pm 2 Weeks, 42 Months \pm 2 Weeks, 45 Months \pm 2 Weeks, 51 Months \pm 2 Weeks and 54 Months \pm 2 Weeks, and 57 Months \pm 2 Weeks after 6-Week Follow-up Evaluation)

Perform the following evaluations:

- Review asthma symptoms, exacerbations, and asthma medication use.
- Solicit adverse events since last follow-up (See Section 8.0).
- Review emergency room visits for respiratory symptoms since last contact.
- Review any hospitalizations for respiratory symptoms since last contact.

7.3.13 Yearly Follow-up (12 Months \pm 4 Weeks, 24 Months \pm 4 Weeks, 36 Months \pm 4 Weeks, 48 Months \pm 4 Weeks and 60 Months \pm 4 Weeks after 6-Week Follow-up Evaluation)

Examine the subject and perform the following evaluations:

- Perform physical exam including body weight, vital signs, pulse oximetry and breath sounds.
- Review asthma symptoms, exacerbations, and asthma medication use.
- Solicit adverse events since last contact.
- Perform pre- and post-bronchodilator spirometry. Pre-bronchodilator spirometry following a 12-hour abstinence from long-acting β_2 -agonist and a 4-hour abstinence from short-acting β_2 -agonists.
- Review emergency room visits for respiratory symptoms since last contact.
- Review any hospitalizations for respiratory symptoms since last contact.

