Follow-up Schedule	A follow-up evaluation will be conducted at 6 weeks after the last treatment session. At this time, the 5 year follow-up phase will begin. Subjects will be contacted via phone every 3 months to solicit for adverse events and asthma status. An in-office follow-up evaluation will be performed annually starting after the 6 week evaluation.
Study Duration	Subjects treated with the Alair System will be followed for 5 years after the final procedure.

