2.1.2 Sample Size

Under the assumption that in the population of US subjects treated with the Alair System the proportion of patients that experience severe exacerbations will be 0.33 (33% of subjects) or less (based on data from AIR2 Trial - 30.9%, 95% CI 24.2%, 37.7%), a sample size of 200 is adequate to demonstrate durability of the treatment effect at 5 years post-Alair treatment. Up to 300 subjects (minimum of 250 subjects) will be enrolled to achieve at least 200 evaluable study subjects, accounting for a 20% drop-out rate over 5 years. To be counted as an evaluable subject, a subject must have either completed the 5-year visit no earlier than the start of the visit

Study Reference Number E7080

window (1797 days) or have at least 1797 days of study follow-up (see Section 2.1.3) and have primary endpoint data at 5 years.

nQuery Advisor Version 7.0 was used to form a basis for the sample size estimation. The “Two group test of equivalence in proportions (large unequal n’s)” procedure based on a one-sided test at alpha equal to 0.05 and a 20% delta was used to generate the powers presented in Table 1. A minimum of 80% power was achieved for all situations wherein the subsequent year’s assumed proportion of subjects with severe exacerbations was 41% or less. The use of independent samples methodology provides a conservative (over-powered) sample size calculation for matched data on a single sample.

Table 1. Two group test of equivalence in proportions (large unequal n’s) [from nQuery Advisor 7.0]

	1	2	3	4	5	6	7	8	9
Test significance level, α (one-sided)	0.050	0.050	0.050	0.050	0.050	0.050	0.050	0.050	0.050
Standard proportion, π_S	0.330	0.330	0.330	0.330	0.330	0.330	0.330	0.330	0.330
Equivalence limit difference, $\pi_T - \pi_S, \Delta_0$	0.200	0.200	0.200	0.200	0.200	0.200	0.200	0.200	0.200
Test expected proportion, π_T	0.330	0.340	0.350	0.360	0.370	0.380	0.390	0.400	0.410
Expected difference, $\pi_T - \pi_S, \Delta_1$	0.000	0.010	0.020	0.030	0.040	0.050	0.060	0.070	0.080
Power (%)	99	99	99	98	97	95	92	88	83
n_S	250	250	250	250	250	250	250	250	250
n_T	200	200	200	200	200	200	200	200	200
Ratio: n_T / n_S	0.800	0.800	0.800	0.800	0.800	0.800	0.800	0.800	0.800
$N = n_S + n_T$	450	450	450	450	450	450	450	450	450

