2.1.3 Statistical Methods

See Section 6.4 for how to identify severe exacerbations.

The proportions of patients with severe exacerbations at each year (p_k , $k=1$ to 5) will be calculated in two ways:

1. Complete Follow-up: using patients who complete the annual follow-up visit or have a follow-up visit (office or phone call) after the visit for that particular year if the annual visit is missed.
2. Complete/Partial Follow-up: using patients who complete the annual follow-up visit no earlier than the start of the follow-up window, have a follow-up visit (office or phone call) after the visit for that particular year if the annual visit is missed, have sufficient follow-up for the year, or had a severe exacerbation during the time period regardless of the amount of follow-up. Sufficient follow-up is having any follow-up visit (office or phone call), adverse event onset date, or hospitalization date that gives the patient at least the number of days of follow-up after the last BT procedure + 42 days given in Table 2.

Table 2. Days for sufficient follow-up by follow-up time

Study Reference Number E7080

Time	Days for sufficient follow-up after the follow-up period starts*
1 Year	337 days
2 Years	702 days
3 Years	1067 days
4 Years	1432 days
5 Years	1797 days

* - the follow-up period starts at last BT procedure + 42 days. The number of days in this column represents the start of the follow-up window after the follow-up period starts and is calculated as # years times 365 days minus 28 days.

All analyses will be done for patients with Complete and Complete/Partial Follow-up. Point estimates and 95% confidence intervals for the proportion of subjects experiencing severe exacerbations during each of the 12-month evaluation periods will be provided. Additionally, the exact upper 95% confidence limit for the difference between the subsequent 12-month proportions and the first 12-month proportion will be calculated, based on methods assuming paired samples; in this analysis, each subsequent 12-month proportion would represent comparisons between the first-year proportion and the second-, third-, fourth-, and fifth-year proportions.

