6.4 Identification of Severe Exacerbations (SE)

1. Filter the medication data (MEDS) to keep all courses of oral corticosteroids (CLASS3=OCS) and other medications that are intravenous uses of the same medications - identify those by looking for CLASS3='Other Specify' and lowercase(CLSSP) with values: 'intravenous corticosteriod' 'intravenous corticosteroid' 'cortcosteroid iv' 'corticosteroid iv'. Note there are spelling mistakes in the entered data.
2. Merge the medication data with the AE data by patient and AE related number (RELAENO) on the medication data with AENUM on the AE data.
3. Use the onset date and the resolution date of the AE to determine the length of the SE. If an AE has no resolution date, impute the date of the most recent follow-up (scheduled or

Study Reference Number E7080

unscheduled) as the resolution date. For partial onset and resolution dates, impute dates as described in Section 6.3.

4. When an AE matches with a course of medication, the AE is considered to be an SE, however, when AEs that are SEs occur too close together, the combined AEs are one SE. If the resolution date of one AE selected as an SE is \leq 6 days before the onset date of another AE that is an SE, then combine the AEs into one SE. There could be more than two AE combined into a single SE.
5. SEs are classified in the time period where the onset date of the SE occurs regardless of the duration of the SE.
6. For each time period, count the number of SEs for each patient and whether the patient has an SE or not. Two types of summaries will be done for the SEs (also ER visits and hospitalization) to include the following patients: (1) patients with the follow-up visit or later visit for that time period, and (2) patients from (1) and patients with any SE in the time period.

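### The SAP's day-1797 rule can exclude a protocol-compliant, event-free 5-year visit from the Complete/Partial Follow-up set and the evaluable count, because protocol and SAP start the clock on different days

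*SAP*

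**What the plan says.** **Visit timing (protocol).** Section 7.3.13 places the 5-year visit at 60 months ± "4 Weeks after 6-Week Follow-up Evaluation". Section 7.3.11 allows that 6-week evaluation to fall a week either side of 6 weeks after the last bronchoscopy. Section 7.3.14 exits the subject once the 5-year evaluation is done. Section 6.5 describes annual visits in 52-week periods starting 6 weeks after the last procedure.

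**Evaluability (SAP).** Table 2 in 2.1.3 counts from a fixed start, last procedure + 42 days, and sets the Year 5 requirement at 1797 days. Section 2.1.2 uses the same number: "a subject must have either completed the 5-year visit no earlier than the start of the visit" window, or have at least 1797 days of follow-up, with Year 5 endpoint data. Section 4.6 uses 365-day years.

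**Analysis sets (SAP 2.1.3).** Item 1, Complete Follow-up, needs the annual visit (or a later contact if that visit was missed) and sets no day limit. Item 2, Complete/Partial, applies the limit: "using patients who complete the annual follow-up visit no earlier than the start of the follow-up window". Its other routes are a later contact after a missed visit, sufficient follow-up by Table 2, or a severe exacerbation (SE) in the period whatever the follow-up. All analyses are run on both sets.

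**Summaries (SAP 6.4, step 6).** There are two populations. The first has the visit or a later one, and the second is "2) patients from (1) and patients with any SE in the time period". Neither has a day limit.

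**The concern.** The protocol window moves with the actual 6-week visit, but the SAP threshold does not. A subject can therefore keep every protocol window and still have the last visit before day 1797.

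Year 5 is where this matters. In Years 1–4 the next 3-monthly call supplies the missing days. After the 5-year visit nothing further is scheduled.

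In Complete/Partial the resulting exclusion depends on outcome: the event-free subject leaves and the subject with an SE stays, which pushes p_5 up. That set, meant as the broader one, then omits someone whom Complete Follow-up and SAP 6.4 include, so two programmers could report different Year 5 proportions from the same records. The count towards the planned 200 evaluable subjects is affected too. Section 2.1.2 as worded has no SE exception, so it loses the subject whatever the outcome.

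**Working it through.** **1. Reproduce the SAP figures.** Table 2 is k × 365 − 28 for k = 1 to 5, which gives 337, 702, 1067, 1432 and 1797, as printed. Table 1, last column, by the unpooled normal approximation: SE = √(0.33 × 0.67/250 + 0.41 × 0.59/200) = 0.0458, and power = Φ(0.12/0.0458 − 1.645) = 83.6% (stated 83%).

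**2. Put the protocol visit on the SAP clock.** SAP day = (day of 6-week visit) + (length of 60 months) + (visit offset) − 42. The 6-week visit lies on days 35–49 and the offset between −28 and +28. Any 60-month span in this study contains one or two leap days, so it lasts 1826 or 1827 days. The SAP's own arithmetic uses 1825.

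| Length of 60 months | Earliest visit, 6-week visit on day 35 | Earliest visit, 6-week visit on day 42 | Nominal visit, 6-week visit on day 35 |
|---|---|---|---|
| 1825 | 1790 | 1797 | 1818 |
| 1826 | 1791 | 1798 | 1819 |
| 1827 | 1792 | 1799 | 1820 |

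The visit fails only if the combined earliness of the two visits exceeds 28, 29 or 30 days respectively. With the 6-week visit on day 42 or later, no in-window visit fails. A visit at the nominal date never fails.

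**3. The 52-week wording.** 5 × 364 = 1820. From day 42, the earliest visit is 1820 − 28 = day 1792, 5 days short. From a day-35 visit it is day 1785, 12 days short.

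**4. How often.** The documents give no distribution of visit dates, so this rests on assumptions. Let c = 0, 1, 2 for 1825, 1826, 1827 days, with the 6-week visit uniform over ± 7 days.

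- 5-year visit uniform over ± 28 days: P = (7 − c)²/(2 × 14 × 56), giving 24.5/784 = 3.1%, 18/784 = 2.3% and 12.5/784 = 1.6%. Counting whole days gives 28, 21 and 15 of 855 pairs (3.3%, 2.5%, 1.8%).
- 5-year visit triangular, centred on the target date: P = (7 − c)³/(3 × 14 × 2 × 28²), giving 343/65856 = 0.5%, 216/65856 = 0.3% and 125/65856 = 0.2%.
- 5-year visit triangular with its peak on the first permitted day: 6.0% with 1825 days. Nothing in the documents supports this shape.
- If sites scheduled in 52-week years from the actual 6-week visit: 78/855 = 9.1% of uniform pairs. Section 7.3.13, which sets the schedule, uses months, so I do not take this as the estimate.

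**5. Effect on p_5 in Complete/Partial.** With a true 33% and a fraction f of event-free subjects dropped, p_5 = 0.33/(1 − 0.67f).

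- f = 1.6%: 33.4%
- f = 2.3%: 33.5%
- f = 3.1%: 33.7%

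In counts, 134 of 200 subjects are event-free. Losing 4 gives 66/196 = 33.7%. Reducing n_T from 200 to 196 in step 1 moves power at 41% from 83.6% to 83.2%. In the paired comparison the shift in the difference is no larger if outcomes in Years 1 and 5 are positively associated, since the dropped subjects then also tend to be event-free in Year 1.

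**The case against.** **The subject is not lost everywhere.** This stands. Complete Follow-up has no day limit, and all analyses are run on it. The loss is confined to Complete/Partial and the 2.1.2 count. The SAP does not name either set as the deciding one, however, so the problem cannot be set aside as belonging to a secondary set.

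**It needs unusual timing.** This also stands: an early 6-week visit must combine with a 5-year visit in the first days of its window.

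**It is small, conservative and covered by the tipping-point analysis.** The first two parts stand. The tipping-point analysis covers the case only by treating as missing a subject whose final visit was made and recorded.

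**The asymmetry comes from the SE exception, not from the clocks.** This is largely right. The exception applies to every early dropout and would survive the fix below. The clock mismatch merely adds compliant subjects to those exposed to it.

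**SAP 6.4 is there to identify exacerbations, not to define analysis sets.** Section 2.1.3 does cite it only for that purpose, and its first population resembles Complete Follow-up. But step 6 states populations for the SE summaries, and its second one differs from Complete/Partial: it has no day limit and no sufficient-follow-up route.

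**A stronger reading that fails.** The SAP summary says "Subjects treated with the Alair System will be followed for 5 years after the final procedure", and protocol 6.8 says "patients will be asked to agree to follow-up evaluations out to 5 years after Alair treatment". A reader might infer that follow-up stops on SAP day 1783–1785 (1825 to 1827 − 42), 12–14 days short, so that no event-free subject could be evaluable. These lines describe duration and commitment loosely. The same SAP summary starts the 5-year phase at the 6-week evaluation, and exit follows the visit timed by 7.3.13. No operative rule ends follow-up at the procedure anniversary.

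**Conclusion.** The inconsistency is real and narrow. A protocol-compliant 5-year visit can fall up to 5–6 days before day 1797 in calendar time (7 days with 365-day years). An event-free subject is then excluded from Complete/Partial and from the evaluable count, although Complete Follow-up and SAP 6.4 include that subject.

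With visits uniform over both windows, 1.6–2.3% of compliant visits are affected (3.1% with 365-day years), and p_5 moves from 33.0% to about 33.4–33.7%. The shapes tried around that assumption run from 0.2% to 6.0%. Against a 20-point margin this is slight, and it makes non-inferiority harder to show.

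Two further inferences are not supported: that subjects seen on their target date are lost, and that the error favours the device. The case for correcting it is that an avoidable, outcome-dependent exclusion sits in a set used for the primary endpoint, and that the SAP's two sets do not nest.

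**What to change.** Change the SAP wording only. No visit needs to move.

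1. In 2.1.2 and 2.1.3 item 2, count as evaluable any 5-year visit made within the protocol 7.3.13 window, or alternatively any subject in Complete Follow-up. The first option rescues every compliant visit. The second also guarantees that Complete/Partial contains Complete, even for visits made before the protocol window opens.
2. In 6.4 step 6, refer to the two sets of 2.1.3 for SEs instead of restating populations.
3. Reconcile the 52-week wording of protocol 6.5 and the duration line in the SAP summary with 365-day years from last procedure + 42 days. A sentence in the SAP saying which clock governs the analysis would do until the protocol text is next revised.

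The cost is a few lines in a SAP revision and a matching change in the derivation program. The SAP is dated June 2016 and protocol section 16.0 projects study completion in December 2019, so on that timeline the change could precede the final Year 5 analysis.

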2 ENDPOINT ANALYSIS

2.1 Primary Endpoint

The primary endpoint will be the proportion of subjects experiencing severe exacerbations during the subsequent 12-month period (for Years 2, 3, 4, and 5) compared to the first 12-month period after the Alair treatment.

Note: Severe exacerbation is defined as worsening of asthma symptoms requiring use of systemic corticosteroids (tablets, suspension, or injection). For subjects already taking oral corticosteroids on a daily or alternate day basis, a severe exacerbation will be defined as a worsening of asthma symptoms requiring any increase in daily dose of systemic corticosteroids. For consistency, courses of corticosteroids separated by 1 week or more will be treated as separate severe exacerbations.

The primary statistical objective is to demonstrate that the proportion of subjects who experience severe exacerbations in the subsequent 12-month follow-up (for Year 2, Year 3, Year 4 and Year 5 [in 12-month periods]) is not statistically worse when compared with the proportion of the first 12-months, which begins 6 weeks after the last Alair treatment. This objective will be met if the upper 95% confidence limit of the difference in proportions (i.e., the subsequent 12-month proportion minus the first 12-month proportion) is less than 20%.

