2.1.1 Hypotheses

The null and alternative hypotheses for the primary endpoint are as follows:

$$H_o : p_k - p_1 \geq 20\%$$

$$H_a : p_k - p_1 < 20\%$$

where p_1 is the proportion of patients with severe exacerbations at 1 year,
 p_k is the proportion of patients with severe exacerbations at k years and
 $k = 2, 3, 4, \text{ or } 5$.

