An exact upper 95% confidence limit of the difference between the subsequent 12-month proportions (for Years 2, 3, 4, and 5) compared to the first 12-month proportion for patients with data at both year 1 and year k that is less than 20% will reject the null hypothesis in favor of the alternative hypothesis and demonstrate that the proportions are not substantially worse during each of the subsequent evaluation periods.

Final conclusions regarding the durability of effectiveness (beyond 1 year) will be based on completing the 5 year follow-up of all subjects who are still in the study at that time.

A sensitivity analysis (tipping-point analysis) will be performed to assess the impact of patients with inadequate follow-up on the evaluations of the primary endpoint. The tipping-point analysis will be on the primary endpoint using matched pairs and will be performed as follows: assuming no loss to follow-up and given the observed number of patients evaluated at 1 year and k years, for all combinations of success/failure for patients with missing data, the primary endpoint will be evaluated until the point at which the conclusion of the study changes.

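### The SAP words success for each of Years 2 to 5 but sizes and powers a single comparison, and never says which rule decides durability

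*SAP*

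**What the plan says.** SAP 2.1 sets one primary objective over Years 2, 3, 4 *and* 5 and gives one criterion, with the limit in the singular: "This objective will be met if the upper 95% confidence limit of the difference in proportions" is less than 20%. Protocol 4.0 and 5.7 carry the same objective.

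SAP 2.1.1 gives one pair of hypotheses indexed by k, where p_k "is the proportion of patients with severe exacerbations at k years and" k is 2, 3, 4 or 5.

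SAP 2.1.3 compares each of the four later years with Year 1. It says that limits below 20% will "demonstrate that the proportions are not substantially worse during each of the subsequent evaluation periods". It adds that final conclusions on durability wait until 5-year follow-up is complete.

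SAP 2.1.2 takes a different view. It says that "a sample size of 200 is adequate to demonstrate durability of the treatment effect at 5 years post-Alair treatment", defines an evaluable subject by Year 5 data, and gives power in Table 1 for one comparison of 250 with 200. It then states: "A minimum of 80% power was achieved for all situations" in which the later year's rate is 41% or less.

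Neither document gives a rule across the four years, a testing order or a multiplicity rule.

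**The concern.** The words *and* and *each of* point to a rule that all four comparisons must pass. The sample size section points to Year 5. The sentence on final conclusions fixes when they are drawn, not which years must pass.

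Two things are at stake. First, mixed results have no agreed interpretation. If Year 3 fails and Year 5 passes, the SAP can be read as supporting either durable or not durable. The tipping-point analysis in SAP 2.1.3 has the same gap, because it runs until the study's conclusion changes and that conclusion is undefined across years. The study is open-label and single-arm, and Protocol 15.0 requires status reports with effectiveness data and an interpretation to date. A rule settled late could therefore be settled with results in view.

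Second, if the success sentence means what it most naturally says, the power in SAP 2.1.2 is not the power of the stated objective.

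**Working it through.** **Inputs from SAP 2.1.2.** Year 1 rate 0.33 ("the proportion of patients that experience severe exacerbations will be 0.33 (33% of subjects) or less"); later rate up to 0.41; 250 subjects at Year 1 and 200 at the later year; and a "procedure based on a one-sided test at alpha equal to 0.05 and a 20% delta was used to generate the powers" in Table 1.

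**Step 1: reproduce Table 1.** For one comparison of independent proportions,

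power = Φ[(0.20 − (p_T − p_S))/SE − 1.645], with SE = √[p_S(1 − p_S)/250 + p_T(1 − p_T)/200].

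At 0.33 and 0.41, SE = √(0.000884 + 0.001209) = 0.0458. Then 0.12/0.0458 = 2.622, and 2.622 − 1.645 = 0.977. Φ(0.977) = 83.6%, against 83% stated. The other columns agree to within one point. Using 0.025 per side gives 74.6%, so the table is per comparison at one-sided 0.05.

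**Step 2: require all four, same inputs.** The four differences share the Year 1 sample, so any two have correlation 0.000884/(0.000884 + 0.001209) = 0.42. Joint power is the probability that all four components of a 4-variate normal with that correlation fall below the Step 1 cut-off.

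| Rate in every later year | One comparison | All four |
|---|---|---|
| 33% | 99.8% | 99.2% |
| 38% | 95.1% | 85.2% |
| 39% | 92.3% | 78.2% |
| 40% | 88.5% | 69.5% |
| 41% | 83.6% | 59.6% |

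Joint power is 81.9% at 38.5%, so it drops below 80% between 38.5% and 39%. With more subjects in the earlier years (238, 225, 213 and 200, an assumption), it is 63% at 41%.

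**Step 3: the paired analysis that SAP 2.1.3 specifies.** The documents give no within-subject correlation, so a range is assumed. Five yearly outcomes per subject were simulated from an exchangeable latent normal, with a one-sided 95% paired Wald limit. Losses are assumed even after Year 1: 238/226/213/200 pairs for 250 enrolled (50 lost) and 285/270/255/240 for 300 enrolled (60 lost). All-four power is as follows; simulation error is about a point.

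| Observed correlation | 0 | 0.1 | 0.2 | 0.3 | 0.4 |
|---|---|---|---|---|---|
| 250 enrolled, constant 41% | 59% | 66% | 73% | 79% | 86–87% |
| 300 enrolled, constant 41% | 69–70% | 76% | 82–83% | 87% | 92% |
| 250 enrolled, rising 35/37/39/41% | 75% | 80% | 85% | 89% | 93% |

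The Year 5 comparison alone, with 200 pairs at 41%, has about 80% power at correlation 0, rising to 94% at 0.4.

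**Step 4: error rate.**
- *Year 5 alone:* 5%.
- *All four:* at most 5%. It is 5.0% when only Year 5 sits at the 20-point margin and about 0.1% when all four do.
- *Any one:* about 15% when all four sit at the margin (15.3% with independent samples, 14% to 15% paired).

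**The case against.** The strongest reply is that SAP 2.1.2 makes no joint claim. It speaks of a single later year, sizes for 5 years and uses the Year 5 evaluable count. On that reading both stated figures hold, and only a label is missing. This stands. A reader might infer that the stated power or error rate fails whichever rule is meant, and the documents do not support that. A Year 5 rule keeps both figures, and an all-four rule keeps the error rate.

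A reader might also take *or* in SAP 2.1.1 to mean that any one year suffices, which would roughly triple the error rate. The text gives this little support. The *or* is index notation defining p_k, while the objective joins the years with *and* and the success sentence says *each of*. It is a reading to rule out, not one that the plan proposes.

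On size, the reply is also fair. A constant 41% is the worst column of Table 1, the expected rate is 33% or less, and Protocol 5.3 names 300 subjects, not 250. A gradual rise or a stronger correlation recovers much of the power. SAP 2.1.2 calls the independent-sample calculation conservative for matched data, but that remark concerns one comparison and does not address the need for four passes.

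Finally, SAP 4.1 plans no formal interim analysis, and final conclusions wait for 5-year data. That reduces the risk of a rule chosen late, but it does not supply the rule.

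**Conclusion.** The gap is real: the wording leans towards all four years, the sizing covers one comparison at Year 5, and no section says which decides. The rule that preserves both stated figures is not the one that the success sentence describes.

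The numerical consequence is limited to the all-four reading and to later rates of about 39% to 41% in every year. There, power at a constant 41% is about 60% on the SAP's inputs. Paired, it is about 59% to 87% with 250 enrolled and 69% to 92% with 300, or 75% to 93% with 250 enrolled and a gradual rise to 41%. At 38% or below on the SAP's inputs, joint power exceeds 80%.

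The paired figures rest on an assumed correlation of 0 to 0.4, an even loss pattern and a Wald limit. The exact limit in SAP 2.1.3 may be somewhat more conservative.

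**What to change.** Before the final analysis, by the amendment route in SAP 4.7, state one rule in SAP 2.1 and 2.1.3:

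- durability is claimed only if the upper limit is below 20% in all four comparisons, which needs no alpha adjustment; or
- Year 5 is the single confirmatory test, with Years 2 to 4 supportive.

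Align the *each of* sentence with the chosen rule and have the tipping-point analysis refer to it. In SAP 2.1.2, label Table 1 and the 80% statement as per comparison. If the all-four rule is chosen, restate the power as joint power with the assumed correlation range.

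The cost is wording and, for the all-four rule, one extra power table and a less favourable stated power. No additional patients or data are needed.
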